6.6.3.1. Exposure to PF-07901801

Phase 1b:

The dose level for PF-07901801 is calculated as actual dose administered/weight (mg/kg). The last available weight of the patient on or prior to the day of dosing will be used.

PF-07901801 will be administered weekly (QW) during Cycle 1, 2, and 3, then bi-weekly (Q2W). Each cycle is 28 days (4 weeks).

Cohort	Dose (mg/kg)
1 (DL1)	4 mg/kg QW for C1 to C3 then Q2W
2 (DL2)	10 mg/kg QW for C1 to C3 then Q2W
3 (DL3)	18 mg/kg QW for C1 to C3 then Q2W

Intended duration of treatment with PF-07901801 (weeks) =

(end date–date of first dose of study drug +1) (days) / 7(days/week),

where end date = start date of last cycle with non-zero dose of study drug + 28 – 1

Duration of exposure to PF-07901801 (weeks) =

(last dose date - first dose date + d) (days) / 7 (days/week),

where d is the number of days based on the maximum number of cycles of PF-07901801 started and defined as following.

- For patients who started 3 cycles or less: d=7 days,
- For patients who started Cycle ≥ 4 : d = 14 days.

Cumulative dose (mg/kg) is the sum of the actual doses of PF-07901801 received.

Intended cumulative dose (mg/kg) is based on the maximum number of cycles of PF-07901801 started and defined as following

- For patients who started no more than 3 cycles:
 - Intended cumulative dose (mg/kg)= $DL(\text{mg/kg}/\text{dose}) * 4 (\text{doses}/\text{cycle}) * \text{Number of Cycles started}$.
- For patients who started maximum Cycle i, where $i \geq 4$:
 - Intended cumulative dose (mg/kg) = $DL(\text{mg/kg}/\text{dose}) * 4 (\text{doses}/\text{cycle}) * 3 (\text{cycles}) + DL(\text{mg/kg}) * 2 (\text{doses}/\text{cycle}) * (i-3) (\text{cycles}) = DL(\text{mg/kg}/\text{dose}) (2i+6) (\text{doses})$

Actual Dose Intensity (DI)

- Overall actual DI (mg/kg/4-week cycle) = [overall cumulative dose (mg/kg)] / [intended duration of treatment with PF-07901801 (weeks)/4].

Relative Dose Intensity (RDI)

- Intended DI (mg/kg/4-week cycle) = [intended cumulative dose (mg/kg)] / [intended duration of treatment with PF-07901801 (weeks)/4]
- Overall RDI (%) = $100 \times [\text{overall actual DI}] / [\text{intended DI}]$

Phase 2:

Up to 2 fixed doses of PF-07901801 will be explored in Phase 2.

The dose level for PF-07901801 is calculated as actual dose administered (mg).

PF-07901801 will be administered weekly (QW) during Cycle 1, 2, and 3, then bi-weekly (Q2W). Each cycle is 28 days (4 weeks).

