Intended duration of treatment with PF-07901801 and duration of exposure of PF-07901801 are calculated in the same way as that for Phase 1b.

Cumulative dose (mg) is the sum of the actual doses of PF-07901801 received.

Intended cumulative dose (mg) is based on the maximum number of cycles of PF-07901801 started and defined as following

- For patients who started no more than 3 cycles:
 - Intended cumulative dose (mg) = $DL(\text{mg/dose}) * 4 \text{ (doses/cycle)} * \text{Number of Cycles started.}$
- For patients who started maximum Cycle i , where $i \geq 4$:
 - Intended cumulative dose (mg) = $DL(\text{mg/dose}) * 4 \text{ (doses/cycle)} * 3 \text{ (cycles)} + DL(\text{mg/dose}) * 2 \text{ (doses/cycle)} * (i-3) \text{ (cycles)}$

Actual Dose Intensity (DI)

- Overall actual DI (mg/4-week cycle) = [overall cumulative dose (mg)] / [intended duration of treatment with PF-07901801 (weeks)/4].

Relative Dose Intensity (RDI)

- Intended DI (mg/4-week cycle) = [intended cumulative dose (mg)] / [intended duration of treatment with PF-07901801 (weeks)/4]
- Overall RDI (%) = $100 \times [\text{overall actual DI}] / [\text{intended DI}]$

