6.6.3.2. Exposure to Tafasitamab

The dose level for tafasitamab is calculated as actual dose administered/weight (mg/kg). The last available weight of the patient on or prior to the day of dosing will be used.

Tafasitamab will be administered at 12 mg/kg IV according to the following schedule: each cycle has 28 days.

- C1: Days 1, 4, 8, 15 and 22.
- C2 and C3 (QW): Days 1, 8, 15 and 22.
- $\geq C4$ (Q2W): Days 1 and 15.

Intended duration of treatment with tafasitamab (weeks) =

(end date–date of first dose of study drug +1)/7,

where end date = start date of last cycle with non-zero dose of study drug + 28 – 1

Duration of exposure to tafasitamab (weeks) =

(last dose date - first dose date + d) (days) / 7 (days/week),

where d is the number of days based on the maximum number of cycles of tafasitamab started and defined as following.

- For patients who started only Cycle 1:
 - d=3, if only Day 1 dose received;
 - d=4, if the last day the dose received is Day 4;
 - d=7, if the last day the dose received is Day 15 or Day 22.
- For patients who started Cycle 2 or 3: d = 7 days;
- For patients who started Cycle ≥ 4 : d = 14 days.

Cumulative dose (mg/kg) is the sum of the actual doses of tafasitamab received.

Intended cumulative dose (mg/kg) is based on the maximum number of cycles of tafasitamab started and defined as following

- For patients who started Cycle 1 only:
 - Planned cumulative dose (mg/kg) = $5*12 \text{ mg/kg} = 60 \text{ mg/kg}$
- For patients who started no more than Cycle 2:
 - Planned cumulative dose (mg/kg) = $5*12 \text{ mg/kg} + 4*12 \text{ mg/kg} = 108 \text{ mg/kg}$
- For patients who started no more than Cycle 3:
 - Planned cumulative dose (mg/kg) = $5*12 \text{ mg/kg} + 4*12 \text{ mg/kg} + 4*12 \text{ mg/kg} = 156 \text{ mg/kg}$
- For patients who started no more than Cycle i , where $i \geq 4$:
 - Planned cumulative dose (mg/kg) = $156 \text{ mg/kg} + (i-3)*2*12 \text{ mg/kg} = 156 \text{ mg/kg} + (i-3)*24 \text{ mg/kg} = (i*24 + 84) \text{ mg/kg}$

Actual Dose Intensity (DI)

- Overall actual DI (mg/kg/4-week cycle) = [overall cumulative dose (mg/kg)] / [intended duration of treatment with tafasitamab (weeks)/4].

Relative Dose Intensity (RDI)

- Intended DI (mg/kg/4-week cycle) = [intended cumulative dose (mg/kg)] / [intended duration of treatment with tafasitamab (weeks)/4]
- Overall RDI (%) = $100\% \times [\text{overall actual DI}] / [\text{intended DI}]$

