6.6.3.3. Exposure to Lenalidomide

The dose level is calculated as actual dose administered (mg/day).

Lenalidomide will be administered 25 mg PO daily on Days 1 through 21 of each 28-day cycle for up to 12 cycles.

Intended duration of treatment lenalidomide (weeks) =

$$(\text{end date} - \text{date of first dose of study drug} + 1) / 7,$$

where end date = start date of last cycle with non-zero dose of study drug + 28 – 1.

Duration of exposure to lenalidomide (weeks) =

$$(\text{last dose date of lenalidomide} - \text{first dose date of lenalidomide} + 7) / 7$$

Cumulative dose (mg) is the sum of the actual doses of lenalidomide received in the study.

Actual Dose Intensity (DI)

- Overall actual DI (mg/4-week cycle) = Cumulative dose (mg) / Duration of exposure to lenalidomide (weeks) / 4 (weeks/cycle)

Intended Dose Intensity (DI)

- Overall intended DI (mg/4-week cycle) = 25 (mg/day) \times 21 (days/4-week cycle) = 525 (mg/4-week cycle).

Relative Dose Intensity (RDI)

- RDI (%) = [Overall actual DI (mg/4-week cycle) / Overall intended DI (mg/4-week cycle)] \times 100% = [Overall actual DI (mg/4-week cycle) / 525 (mg/4-week cycle)] \times 100%

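### The lenalidomide actual dose intensity formula lacks the brackets used for the other two drugs; coded as written, actual and relative dose intensity come out 16 times too small

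*SAP*

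**What the plan says.** SAP 6.6.3.3 gives the lenalidomide schedule as follows: "Lenalidomide will be administered 25 mg PO daily on Days 1 through 21 of each 28-day cycle for up to 12 cycles". It defines the actual DI as "Overall actual DI (mg/4-week cycle) = Cumulative dose (mg) / Duration of exposure to lenalidomide (weeks) / 4 (weeks/cycle"). The intended DI is "Overall intended DI (mg/4-week cycle) = 25 (mg/day") times "21 (days/4-week cycle) = 525 (mg/4-week cycle"). RDI is the actual DI divided by the intended DI, as a percentage. Duration of exposure in weeks is last dose date minus first dose date plus 7 days, divided by 7.

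The corresponding lines for the other two drugs carry brackets:

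- PF-07901801, Phase 1b (SAP 6.6.3.1): "Overall actual DI (mg/kg/4-week cycle) = [overall cumulative dose (mg/kg)] / [intended duration of treatment with PF-07901801 (weeks)/4"].
- PF-07901801, Phase 2 (SAP 6.6.3.1): "Overall actual DI (mg/4-week cycle) = [overall cumulative dose (mg)] / [intended duration of treatment with PF-07901801 (weeks)/4"].
- Tafasitamab (SAP 6.6.3.2): "Overall actual DI (mg/kg/4-week cycle) = [overall cumulative dose (mg/kg)] / [intended duration of treatment with tafasitamab (weeks)/4"].

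Nothing elsewhere in the SAP or protocol restates or corrects the lenalidomide line.

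**The concern.** Converting milligrams per week to milligrams per 4-week cycle means multiplying by 4, which is the same as dividing the dose by the number of 4-week cycles (weeks/4). Without brackets, the lenalidomide line divides by 4 instead. Its units are then mg × cycle/week², not the stated mg per 4-week cycle, yet the next step compares it with 525 mg per 4-week cycle.

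SAP 6.6.3 presents these formulae as the ones to apply to each drug separately, so this line is the programming instruction for lenalidomide. If it were followed as written, fully dosed participants would be reported with an RDI of about 6%. A second programmer working from the same text could reproduce the error. Lenalidomide is also the drug that Protocol 6.6 restarts at a lower dose after shared hematologic toxicity, so its RDI is a natural place to look for the tolerability of the combination.

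**Working it through.** **Inputs, all from SAP 6.6.3.3.** 25 mg on 21 of every 28 days; duration of exposure = (last dose date − first dose date + 7)/7 weeks; cumulative dose = sum of doses taken.

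**The plan's own figure.** Intended DI = 25 × 21 = 525 mg per 4-week cycle. This reproduces.

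**Set-up for k fully compliant cycles on schedule.**

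- Cumulative dose = 525k mg.
- First to last dose = 28(k − 1) + 20 days.
- Duration of exposure = (28k − 1)/7 weeks.

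**The two readings.**

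- Literal: DI = dose / weeks / 4 = dose / (4 × weeks).
- Bracketed: DI = dose / (weeks/4) = 4 × dose / weeks.

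Their ratio is 4 × 4 = 16 for any dose and any duration.

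**Numbers.** RDI = DI/525.

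| Case | Dose (mg) | Days counted | Weeks | Literal DI | Literal RDI | Bracketed DI | Bracketed RDI |
|---|---|---|---|---|---|---|---|
| 1 cycle | 525 | 27 | 3.857 | 34.03 | 6.48% | 544.4 | 103.7% |
| 2 cycles | 1050 | 55 | 7.857 | 33.41 | 6.36% | 534.5 | 101.8% |
| 6 cycles | 3150 | 167 | 23.857 | 33.01 | 6.29% | 528.1 | 100.6% |
| 12 cycles | 6300 | 335 | 47.857 | 32.91 | 6.27% | 526.6 | 100.3% |
| 6 cycles, 25 mg in Cycle 1 then 20 mg | 2625 | 167 | 23.857 | 27.51 | 5.24% | 440.1 | 83.8% |

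For example, the one-cycle literal value is 525/3.857/4 = 34.03, and 34.03/525 = 6.48%. In the reduced-dose row the dose is 525 + 5 × (20 × 21) = 525 + 2100 = 2625 mg.

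**Why the bracketed RDI slightly exceeds 100%.** This is a separate, small effect. The +7 convention counts 27, 167 and 335 days for 1, 6 and 12 full cycles, one day short of 28, 168 and 336. Adding 8 instead, with the last dose on Day 21 of the final cycle, gives 4, 24 and 48 weeks and an RDI of 100.0% each time. The intended duration of treatment, which SAP 6.6.3.3 defines but does not use in the DI line, gives the same weeks when cycles start on schedule.

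**The case against.** The strongest reply is that this is a slip of notation which the line itself resolves. Each term carries its unit: weeks divided by weeks per cycle gives cycles, and milligrams divided by cycles gives the stated label. Only that grouping fits the label, the 525 comparator and the sister formulas. A programmer would have to overlook all three, and a reviewer would have to accept an RDI near 6% in compliant participants. This stands as a limit on likelihood. It does not make the line correct as written.

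The sister lines are also not the same formula: they divide by intended duration of treatment, whereas the lenalidomide line divides by duration of exposure. That is true. They support the grouping, not the choice of duration.

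The reach is narrow as well. Intended DI, cumulative dose and duration of exposure are unaffected; only actual DI and RDI change. DLT evaluability rests on the percentage of planned dose received (Protocol 4.3.4 and 9.2.1.1), not on RDI. Phase 2 will not be run (Protocol 9), and lenalidomide reductions and interruptions are summarized separately (SAP 6.6.3.4 and 6.6.3.5). All of this stands and fixes the severity as minor.

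Finally, a stacked fraction could have been flattened when the PDF was read. This cannot be fully excluded, but square brackets survive in the RDI line of the same section and in the DI lines for the other drugs, so it is unlikely.

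**Conclusion.** The concern holds, as a minor point. Taken literally, the formula gives a lenalidomide actual DI and RDI that are each too small by a factor of exactly 16, whatever the dose or duration. At full compliance the RDI would read 6.48% after one cycle and 6.27% after twelve.

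The factor of 16 needs no assumption beyond normal operator order. The percentages assume every scheduled dose is taken and cycles start on schedule. The harm depends on the line being coded as written, and nothing in the documents shows whether it has been. The effect stays within the descriptive exposure tables for Phase 1b; no endpoint, estimand or dose decision depends on it.

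**What to change.** In SAP 6.6.3.3, write the lenalidomide actual DI as [cumulative dose (mg)] / [duration of exposure to lenalidomide (weeks)/4], and confirm that the analysis program groups the terms in that way. The cost is one pair of brackets in one line and a short program check. No other formula needs to change.

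Optionally, the sponsor may review the duration used. With the +7 convention the bracketed RDI at full compliance runs from 103.7% at one cycle to 100.3% at twelve. Adding 8 days gives 100% when the last dose falls on Day 21 of the final cycle; the intended duration already defined in that section gives 100% when cycles start on schedule and would match the other two drugs. That would change a definition as well as the brackets, and it is not needed to remove the factor of 16.

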6.6.3.4. Dose reductions

Applicable to PF-07901801 and tafasitamab. Dose reduction is defined as actual non-zero dose < 90% of the planned dose.

Applicable to lenalidomide. Dose reduction is defined as a change to a non-zero dose level lower than that planned in the protocol.

The number and percentage of patients with at least one dose reduction as well as a breakdown of the number of dose reductions (1, 2, 3, ≥ 4) will be summarized.

6.6.3.5. Dose interruptions

Applicable to lenalidomide.

An interruption is defined a 0 mg dose administered on one or more days for lenalidomide on Days 1 through 21 of each 28-day cycle. What follows defines how dose interruptions will be counted in the case of multiple dose interruptions.

- If an interruption occurs consecutively for at least two days, then it will be counted only once (example: If the actual dose on days 1-3 is 25 mg and actual dose on days 4-5 is 0 mg and dose interruption on days 4-5 is due to AE, then the total number of dose interruptions is 1).
- If an interruption occurs for more than one day but the days are not consecutive, ie there is at least one dosing day in between, then each dose interruption will be counted as a different occurrence (example: If the actual dose on days 1, 3 and 5, is 25 mg and actual dose on days 2 and 4 is 0 mg the total number of dose interruptions is 2).

A dose interruption is not considered a dose reduction.

The number and percentage of patients with dose interruptions and the corresponding reasons will be summarized.

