## Administration

Study interventions will be administered in 28-day cycles. Lenalidomide will be administered up to C12 while PF-07901801 and tafasitamab will be administered until PD, non-tolerable toxicity, or death. PF-07901801 will be administered by intravenous (IV) infusion weekly for the first three cycles and then every two weeks for Cycle 4 and beyond. Participants will receive different dose levels as per assigned cohort.

Tafasitamab will be administered 12 mg/kg IV on Days 1, 4, 8, 15 and 22 in Cycle 1, weekly for Cycle 2 and 3 and then every 2 weeks for Cycle 4 and beyond. Lenalidomide will be administered 25 mg PO daily on Days 1 through 21 of each 28-day cycle for up to 12 cycles.

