**Table 8. Dose Modifications for Lenalidomide Toxicities**

Criteria	Severity	Dosage modification
Tumor flare reaction (related)  Kidney toxicities as per CTCAE v5.0 (test can be repeated after proper hydration, if needed) (related or unrelated)	G3/4	
 
Interrupt lenalidomide dosing.
 
Provide symptomatic treatment as per local guidelines.
 
Continue other study interventions after discussion with the sponsor.
 

	Toxicities resolve to $\leq$ G1	
 
Restart lenalidomide (maintain same dose level).
 

	G2	
 
Reduce lenalidomide to 10 mg once daily.
 

	G3 not requiring dialysis	
 
Administer lenalidomide at 15 mg every other day.
 
Discontinue lenalidomide if dialysis is required.
 

	G4	
 
Discontinue lenalidomide.
 

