6.6.3. Study Treatment Exposure and Compliance

The following analyses will be based on the safety analysis set by treatment group.

Cycle definitions for study drugs that are administered in combination apply to all the study drugs in the combination. Ie, cycle is patient-dependent, rather than study-drug-dependent when study drugs are administered in combination.

For Cycle X, actual cycle start date for each patient is

- the earliest start date of dosing in the Cycle X day 1 visit eCRF exposure page, if the patient received study treatment on that visit (ie, any study drug with dose>0 at that visit)
- the first day of assessments in the Cycle X day 1 visit, if the patient did not receive study treatment on that visit (ie, all study drugs had dose=0 at that visit). Use start date in the exposure page if available; if start date is not available then use date of collection of vital signs on Cycle X day 1 visit.

Actual cycle end date for each patient is,

- for all cycles X except the last cycle, actual cycle end date = actual cycle (X+1) start date – 1 day;
- for the last cycle, actual cycle end date = actual cycle start date + 28 (in days) – 1 day

Cycle duration (weeks) = (actual cycle end date – actual cycle start date + 1)/7

When summarizing exposure for each study drug, only cycles from first dose of study treatment until the last cycle with non-zero dose of at least one of the study drugs should be included.

Exposure will be summarized as dose received (duration of exposure, cumulative dose, actual dose intensity) and as dose received relative to intended dose (relative dose intensity [RDI]).

The information that will be summarized depends on how the study drug is dosed (eg, infusion cyclical, oral daily, oral cyclical).

The formulae below should be applied to each study drug separately even when study drugs are administered in combination.

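### SAP 6.6.3.5 does not exclude protocol-specified zero-dose days, or days after lenalidomide is completed or permanently stopped, from its count of lenalidomide dose interruptions

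*SAP*

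**What the plan says.** SAP 6.6.3.5 defines a lenalidomide interruption as "a 0 mg dose administered on one or more days for lenalidomide on Days 1 through 21 of each 28-day cycle". Two counting rules follow, each with an example. For runs of zero days: "If an interruption occurs consecutively for at least two days, then it will be counted only once". For zero days separated by a dosing day, each counts separately; in that example, the "actual dose on days 2 and 4 is 0 mg the total number of dose interruptions is 2". The output is stated as follows: "The number and percentage of patients with dose interruptions and the corresponding reasons will be summarized".

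Four other places bear on the rule:

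- SAP 6.6.3.3 gives the planned schedule: "Lenalidomide will be administered 25 mg PO daily on Days 1 through 21 of each 28-day cycle for up to 12 cycles".
- The Protocol synopsis (Administration) lets the other two drugs run on: "Lenalidomide will be administered up to C12 while PF-07901801 and tafasitamab will be administered until PD, non-tolerable toxicity, or death".
- SAP 6.6.3 says that, for each drug's exposure summary, cycles from first dose "until the last cycle with non-zero dose of at least one of the study drugs should be included".
- Protocol Table 8, for Grade 3 kidney toxicity not requiring dialysis, says: "Administer lenalidomide at 15 mg every other day".

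**The concern.** The rule asks only whether the dose was 0 mg, not whether a dose was due. Its neighbours do refer to the plan: SAP 6.6.3.4 compares the dose given with the planned dose or level, and SAP 6.6.3.6 subtracts the planned interval between doses.

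Three kinds of zero-dose day are therefore not excluded:

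1. Days inside Days 1-21 on which the protocol itself calls for no dose, as under the every-other-day regimen.
2. Days after the planned maximum of 12 cycles, while PF-07901801 and tafasitamab continue.
3. Days after a permanent lenalidomide stop, while the other drugs continue. The footnote to Protocol Table 10 foresees this situation.

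The percentage of patients with an interruption could then mix true holds with adherent dosing, planned completion and discontinuation. Permanent stops would also be reported twice, because SAP 6.6.2.1 already tabulates discontinuation separately for each drug.

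**Working it through.** The check applies the rule as a count of runs of 0 mg within Days 1-21. SAP 6.6.3.5 does not say how a run that crosses from one cycle to the next is counted, so two readings are shown: (a) runs counted within each cycle, and (b) a run ended only by a dosing day. The last column applies the rule proposed under the fix, taking the recorded stop date as the date of the last dose.

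| Schedule | (a) | (b) | Proposed |
|---|---|---|---|
| SAP example: 0 mg on days 4-5 | 1 | 1 | 1 |
| SAP example: 0 mg on days 2 and 4 | 2 | 2 | 2 |
| 12 full cycles, 0 mg only on Days 22-28 | 0 | 0 | 0 |
| Every other day from Day 1, one cycle | 10 | 10 | 0 |
| 12 full cycles, other drugs to Cycle 18, 0 mg held for later days | 6 | 1 | 0 |
| Permanent stop after the Cycle 5 Day 9 dose, other drugs to Cycle 8, 0 mg held for later days | 4 | 1 | 0 |
| Hold from Day 18 to Day 3 of the next cycle, then resumed | 2 | 1 | 1 |

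The first two rows reproduce the SAP's own figures. The others follow by counting:

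- **Every other day:** dosing on odd days gives (21 + 1)/2 = 11 dosing days and 21 - 11 = 10 zero days. No two zero days are adjacent, so there are 10 runs.
- **Completed course:** 18 - 12 = 6 later cycles, which is 6 runs under (a). Under (b) they form one unbroken run.
- **Permanent stop:** the rest of Cycle 5 plus Cycles 6, 7 and 8 gives 1 + 3 = 4 under (a) and 1 under (b).
- **Hold across the rest week:** Days 18-21 and the next Days 1-3 are two runs under (a) and one under (b).

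SAP 6.6.3.5 tabulates patients, not occurrences. The figure that matters is therefore whether a count exceeds zero. The every-other-day participant is flagged under either reading. The completed course and the permanent stop are flagged only if 0 mg values exist or are derived for the later days. The rest-week hold is a true interruption and is flagged either way, so the unsettled counting there does not alter the table.

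Size of one wrong flag, using the numbers in Protocol 4.1 and 9.6:

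- All of Phase 1b, about 20 participants: 1/20 = 5 percentage points.
- A dose level with 2 to 4 participants: 1/2 = 50 down to 1/4 = 25 points.
- The MTD or highest safe tested level with 6 to 9 participants: 1/6 = 17 down to 1/9 = 11 points.

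**The case against.** The strongest reply is that the later zeros may never exist. Protocol 6.5 has the dosing diary kept while the participant is on lenalidomide, and the Schedule of Activities collects it through Cycle 12 or end of treatment. The cycle-inclusion sentence in SAP 6.6.3 is followed by a definition of exposure as duration, cumulative dose and dose intensity, without mention of interruptions. A programmer could also read each cycle as each lenalidomide cycle. The documents keep stopping apart from interrupting: SAP 6.6.2.1 has per-drug disposition, and SAP 6.7.1 separates drug interrupted from drug withdrawn. This stands as far as it goes. A reader might infer that every completed course and every permanent stop will be counted, and the documents do not establish that. They do not exclude it either: SAP 6.6.3 provides for visits at which all drugs have dose 0, and the classification should not depend on how such days are entered.

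Other parts of the reply also stand:

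- The scheduled rest week is already outside the Day 1-21 window.
- The SAP's alternating-day example uses 25 mg, so it illustrates missed daily doses. It shares the pattern of zero days with Table 8 but not the regimen.
- The Table 8 case needs Grade 3 kidney toxicity, and Phase 1b entry requires creatinine clearance of at least 60 mL/min, so few participants may reach it.
- Some participants would be flagged anyway for genuine holds. Protocol Table 6 withholds lenalidomide for specified cytopenias, and Protocol section 2 cites Grade 3 or higher neutropenia in 48% of patients on tafasitamab plus lenalidomide. The net number of wrong flags is smaller than the number of participants to whom the rule misapplies.

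A reader might also infer that tolerability by dose level can no longer be described. That does not follow: reasons are reported beside the interruptions, and SAP 6.7.1.1 and 6.7.1.3 tabulate adverse events leading to lenalidomide interruption by treatment group from the adverse event page, independently of this derivation.

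**Conclusion.** The concern holds as a defect in a stated rule, of minor weight. Followed as written, SAP 6.6.3.5 gives a wrong result for an adherent every-other-day participant; this assumes only that scheduled off-days are held as 0 mg. For completed courses and permanent stops the result is possible but not shown: it needs 0 mg values for days after lenalidomide ended, and a reading of SAP 6.6.3 that carries those cycles into the interruption table.

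The consequence is confined to one descriptive table of patients and reasons. The number of wrong flags cannot be estimated from the documents; each adds about 5 percentage points overall in Phase 1b and 11 to 50 points within a dose level of 9 down to 2 participants. Phase 2 will not be initiated, so Phase 1b is where this applies.

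**What to change.** Reword SAP 6.6.3.5 along these lines:

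- An interruption is one or more days within Days 1-21 of Cycles 1-12 on which the protocol dosing schedule applicable to that participant, including a Table 8 every-other-day schedule, called for a non-zero lenalidomide dose and 0 mg was taken.
- Days on hold for toxicity or any other reason count as interruptions, including holds that are ongoing at data cutoff or that end in discontinuation.
- Only days after the recorded date of permanent lenalidomide discontinuation or completion are excluded. Name the CRF field that supplies this date.
- Days 22-28 are ignored when judging whether zero-dose days are consecutive, so a hold across the rest week counts once.

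Two simpler cut-offs should be avoided. Counting only up to the last non-zero lenalidomide dose would lose toxicity holds that lead to discontinuation or are still open at cutoff. Counting only days when a dose was currently prescribed could remove ordered holds altogether.

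The cost is SAP wording and one derivation. No new data are needed if the CRF identifies participants on an every-other-day schedule and the dates it applied. Protocol 6.5 already requires start and stop dates and the dates of interruptions and reductions; the documents do not show whether the schedule itself is recorded, and this should be checked.
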